# I. Introduction

## 1.1 Background and rationale

Adolescence is a critical period of physical and psychological development and for achieving human potential. Rapid physical, psychosocial and cognitive growth and development is coupled with increased energy and nutrient requirements (Das et al., 2017; Spear 2002). Poor nutrition during adolescence can have adverse consequences impacting health in adulthood. The significance of nutrition during adolescence is especially important for girls, as poor nutrition can affect their well-being as well as the survival, health and well-being of their children (Das et al. 2017). Data and evidence on the nutritional status of adolescents in low- and middle-income countries is scarce, even though they represent some 1.8 billion individuals. Globally, the health and nutrition status of adolescents have only modestly improved over the last 50 years (Akseer et al. 2017).

In Ethiopia, where the population is very young with 40 percent under the age of 15 years (UNDP 2017), evidence on the nutrition of adolescent girls and their determinants is limited as literature tends to focus on issues of child marriage, education, economic empowerment, and sexual and reproductive health (Stavropoulou and Gupta-Archer 2017). There is, however, growing recognition of the importance of adolescent health and well-being (Patton et al. 2016). In 2015, the UN Secretary-General's Global Strategy for Women's, Children's, and Adolescents' Health was launched, in part, to include adolescents as a focus of the new Sustainable Development Goals. The federal government of Ethiopia has adopted a package of adolescent nutrition interventions into national guidelines (see Ethiopia's Federal Ministry of Health (FMOH) *National Guideline on Adolescent, Maternal, Infant and Young Child Nutrition*).

Alive & Thrive (A&T) is an initiative that supports the scaling up of nutrition interventions to save lives, prevent illnesses, and contribute to healthy growth and development through improved maternal nutrition, breastfeeding and complementary feeding practices in several countries. In October 2017, A&T was awarded by the Bill & Melinda Gates Foundation's Ethiopia Office a new five-year agreement to Accelerate Improvements in Maternal, Adolescent, Infant and Young Child Nutrition in Ethiopia. The A&T Ethiopia 3.0 investment (2018–2022) will support the government of Ethiopia to achieve targets set out in the national nutrition program (NNP II) and the National Nutrition Sensitive Agriculture Strategy (NNSAS). A&T will focus its role on strengthening systems at the national and regional level for achieving large scale and sustainability, and strengthening the evidence base for programs and policies.

In Ethiopia, A&T will test the feasibility of implementing a package of locally tailored adolescent nutrition interventions through school-based (in-class curriculum, extracurricular activities, parent-teacher associations and activities) and community platforms. The impacts of these nutrition-focused interventions will be compared with standard school and community activities in control areas.

## 1.2 Objectives

To evaluate the feasibility and impact of delivering nutrition interventions through school-based platforms on diet quality among adolescent girls.

Research questions for the evaluation include:

- 1) Is it **feasible** to integrate locally relevant adolescent nutrition interventions through school-based platforms?

- 2) What are the **barriers and opportunities** for strengthening school-based nutrition interventions for adolescents?
- 3) What are the impacts of interventions on the **quality of diets** (dietary diversity and less consumption of unhealthy snacks) among adolescent girls?

### 1.3 Trial design

The evaluation will use a two-arm cluster-randomized, non-masked trial design, consisting of two cross-sectional surveys at baseline and endline. The unit of randomization is the primary school which includes grades 1-8. The baseline survey will take place in October-November 2019 (when the school year begins), and the endline survey will place in March-April 2021 (following the end of first semester classes). Program implementation was halted from March to October 2020 due to the COVID-19 pandemic, thus the endline survey was postponed to the following school year after implementation was reinitiated. The study design will allow us to assess the impact of adolescent nutrition interventions delivered through school on adolescent girls aged 10-14 years enrolled in grades 4-8.

[figure not shown]
## II. Methods: Participants, Interventions and Outcomes

### 2.1 Study setting

Implementation of the adolescent nutrition study will take place in two regions: Southern Nations Nationalities and People's Region (SNNPR), a primarily agrarian region, and Somali, a region with a high population of pastoralists (see **Figure 1**). The Somali region is among the poorest of Ethiopia's nine administrative regions, predominantly rural, and relatively ethnically homogeneous. According to the most recent Ethiopian census in 2007, 38 percent of the population in Somali is pastoral compared with less than one percent in SNNPR (CSA 2007). SNNPR is one of the most populous regions in Ethiopia as well as the most diverse; more than 80 ethnic groups reside in the region.

Study regions were selected at the request of the Government of Ethiopia, so that adolescent nutrition intervention packages be tested in both agrarian and pastoral settings. Pastoralists—agriculturalists who rely primarily on their livestock for their food and income—and the regions they live have had few opportunities to be studied in the past. Their migratory nature makes it particularly difficult to track them through surveys. Policymakers are requesting programmatic experience across regions so that results and interventions can be used for the scale-up of nationally accepted guidelines and targets. Current guidelines for the primary school system are standardized nationwide, providing further incentive to include diverse areas for study implementation.

Figure 1. Study regions

Net primary school attendance is moderate nationwide, but lower in the Somali region: the net attendance ratio (percentage of official primary school-age population that attends primary school) is 73.8 in SNNPR and 59.2 in Somali (compared to 71.3 nationwide) (see **Table 1**). While there is gender parity in primary school attendance in SNNPR, the net attendance ratio for girls is 5.9 percentage points lower than the ratio for boys in Somali. Though not ideal, primary schools offer one of the few opportunities for the government to reach a substantial number of adolescent girls in the 10 to 14-year age group through nationally scaled up programs.

School dropout is a serious concern; in 2014, 61.8 percent of students who started primary school dropped out between the first and last grade (World Bank EdStats, 2019). Dropout rates are roughly the same for boys (62.7 percent) and girls (60.7 percent). Primary school-life expectancy is 6.2 years (6.4 for boys and 5.9 for girls). In 2015, there were more than 2.2 million children of primary school age who were not in school, 60.8 percent of which were girls (World Bank EdStats, 2019). The desirability of sending girls to school may be improved through additional services such as adolescent nutrition-related activities.

Information on dietary diversity among adolescent girls and boys 10-14 years of age is unavailable in the 2016 EDHS. However, body mass index (BMI) indicators are available for boys and girls ages 15-19 years of age. A low BMI can indicate eating too little or having an unbalanced diet that lacks adequate nutrients. Roughly 45 percent of adolescent girls in Somali and 17.4 percent of adolescent girls in SNNPR are thin (BMI <18.5 kg/m^2). Thinness is more common among adolescent boys: 78.1 percent are thin in Somali and 45.2 percent are thin in SNNPR.

Information on dietary intake is critical for appropriate planning of interventions that can effectively improve the diets and nutritional status of adolescents. But few studies have assessed dietary diversity among adolescents and school-aged children in Ethiopia. Those that have are limited to specific regions and towns across the country. Of the studies reviewed by a recent A&T landscape analysis of adolescent health and nutrition in Ethiopia, mean dietary diversity scores ranged from 3 food groups (Herrador et al. 2014) to 7 (Gali et al. 2017), with the average scores across studies being 4.5 food groups (Truebwasser 2017). Knowledge of healthy food choices among adolescents may also be limited. A Knowledge, Attitudes and Practice (KAP) survey conducted in several regions (including SNNPR and

Somali) of Ethiopia found that only two thirds of adolescent girls reported hearing about balanced diets. In Somali, 85 percent had not heard about balanced diets (FMoH and UNICEF, 2016).

Across SNNPR and Somali regions, A&T selected seven woredas (districts) as potential intervention areas on the basis of having adequate school access and infrastructure. Four woredas were selected in SNNPR and three woredas in Somali region. In Somali, woredas with more settled communities and less security issues were selected; fewer woredas were also selected, compared with SNNPR, as the communities are more homogenous. The list of study woredas and their corresponding total numbers of primary schools with grades 1-8 are presented in **Table 1**.

Table 1. Study woredas and total number of primary schools available

No.	Region	Zone	Woreda	Population	Kebeles	Primary Schools with grades 1-8
1	Somali	Fafan	Gursum	37,425	15	11
2		Fafan	Harawa	32,034	16	9
3		Fafan	Keberi Beyah	165,518	29	15
4	SNNPR	Gurage	Sodo	175,400	54	32
5		Gurage	Muhor Na Aklil	119,137	29	34
6		Silti	Dalocha	89,807	18	19
7		Kembata Tembaro	Doyo Gena	78,634	18	23

## 2.2 Eligibility criteria

To be eligible for inclusion in the study, adolescent girls must be enrolled in the study primary school, be between 10 to 14 years of age (grades 4-8) and have received parental consent and given assent to participate in the study. Adolescent girls will be excluded if they or their parent/guardian are unwilling to participate in any part of the baseline or endline surveys.

At the school level, the principal and science teacher, and health extension workers (HEW) responsible for providing nutrition education or facilitating other related activities/interventions and have given informed consent will be interviewed.

## 2.3 Interventions

The package of locally tailored adolescent nutrition interventions will include in-school education about nutrition and healthy food choices, mentoring and peer group activities related to nutrition, and parent education on adolescent nutrition during school and community meetings. Intervention components are presented in **Table 2**.

Table 2. Description of interventions for treatment and control primary schools

CORE INTERVENTIONS	INTERVENTION PRIMARY SCHOOLS	CONTROL PRIMARY SCHOOLS
At school:		

 
Classroom education about healthy diet and nutrition
 
	Classroom lessons related to nutrition, dietary diversity, healthy food choices and hand washing	Standard health education

 
Flag events or assemblies about healthy diet and nutrition
 
	Flag events or school assemblies led by principals to provide messages on nutrition, dietary diversity, healthy food choices and hand washing	Standard flag ceremonies or assemblies

 
Peer group mentoring on healthy diets and nutrition
 
	Selected adolescent girls are mentored by science teachers as peer mentors and hold weekly group discussions with other girls to discuss nutrition, dietary diversity, healthy food choices and handwashing	None

 
BMI measurement and counseling
 
	Trained science teachers take anthropometric measurements of adolescent girls to calculate BMI and provide nutrition counseling	None
Parent-teacher meetings	Parent-teacher meetings to inform and encourage parents about adolescent nutrition, dietary diversity, healthy snacks, and handwashing	Parent-teacher associations focused on school performance and management
Home visits by health workers	Home visits by HEWs and/or community volunteers to discuss with parents about adolescent nutrition, dietary diversity, i healthy food choices, and handwashing	Home visits for routine health services
Community gatherings to discuss adolescent nutrition	Community gatherings by HEWs and meetings with religious leaders to discuss with parents about adolescent nutrition, dietary diversity, healthy food choices, and handwashing	None
Training for school staff and other actors	Workshop on the adolescent nutrition interventions above for school principals, science teachers, HEWs, supervisors, and woreda officers	Standard education training
Supportive supervision for school staff and other actors	Biweekly supportive supervision on adolescent nutrition activities for schools and HEWs by school supervisors or woreda health/education office	Standard school supervision

## 2.4 Outcomes

The primary outcome of the study focuses on diet quality measures:

### 1) Dietary diversity among adolescent girls

- i. Mean number of food groups consumed by adolescent girls
- ii. Proportion of adolescent girls who achieve minimum dietary diversity (at least 5 food groups)

The secondary outcomes relate to exposure to and utilization of key nutrition interventions, as well as service provider capacities. These include:

- 2) Meal frequency and healthy food choices among adolescent girls (less consumption of sugary drinks and salty/fatty processed foods)
- 3) Exposure to nutrition interventions at school and to nutrition information from school, health workers, and other sources among adolescent girls and their parents
- 4) Nutrition knowledge and handwashing knowledge and practices among adolescent girls and their parents

- 5) School teacher, principal and HEW knowledge on benefits and intervention content for dietary diversity and healthy foods/snacks, and handwashing
- 6) Availability of resources (educational materials, healthy food environments, and training and supportive supervision for teachers/staff)

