## 2.6 Sample Size

The primary study sample is adolescent girls enrolled in primary school and aged 10-14 years (grades 4-8). The sample size was estimated based on current prevalence of the primary outcome, the expected change after intervention, power to detect those differences (80%), and level of significance ( $\alpha=0.05$ ). As the intervention was randomized at the cluster level (54 clusters) rather than the individual level, cluster effect was considered for sample size calculation.

We used the number of food groups from the A&T Phase 1 endline survey for SNNPR (mean: 3.26, SD: 1.40, categorized as 9 food groups; Arimond et al., 2010), assuming an intra-cluster correlation (ICC) of 0.18. We calculated that a minimum sample of 189 girls per group will be able to detect a minimum of 0.6 food group consumption increase. The sample size at endline will be rounded to 270 girls per group so that 10 girls per school (2 per grade) will be sampled. Based on baseline data, we observed a mean of 3.69, SD: 1.56, categorized as 10 food groups. Assuming an ICC of 0.015, we estimated that this sample size will detect a minimum difference of 0.5 food groups.

School principals, science teachers and HEWs responsible for providing nutrition education or facilitating other related activities/interventions will also be included in both baseline and endline surveys.

At baseline, a light data collection at schools and subsamples of adolescent girls and their parents will be conducted to assess comparability between study arms. At endline, the full samples of adolescent girls and their parents will be surveyed (including those who participated at baseline).

Thus, the overall study samples are presented in **Table 3**.

Table 3. Sample sizes

	Baseline 2019		Endline 2021	
	Intervention	Control	Intervention	Control
Adolescent girls	81	81	270	270
Parents of adolescents	81	81	270	270
Principals (1 per school)	27	27	27	27

Science teachers (1 per school)	27	27	27	27
HEWs (1 per school)	27	27	27	27
Total	243	243	621	621

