### 4.4 Statistical methods

Data analysis will use econometric analysis to control for (any) differences at baseline and between intervention and comparison groups for all relevant variables of interest. Statistical testing for differences between the two groups will be done using a random effects regression, accounting for the clustering of errors within and across schools.

The randomized study design allows for the identification of causal effects of the adolescent nutrition intervention through comparisons of mean outcomes between the treatment and control groups. Key indicators will include dietary diversity. Impact will be assessed using “difference-in-difference” (DID) estimation and/or analysis of covariance (ANCOVA) controlling for covariates. Data management, data cleaning and statistical analyses will be conducted using Stata version 16 (Statacorp, USA). The statistical significance for tests will be set at 5% for main effects or 10% in case of interactions. All statistical tests will be one-sided.

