## 1.3 Study sample

The primary study sample is adolescent girls (AG) aged 10-14 years and enrolled in grades 4-8 in the current school year. We estimated a total sample size of 540 girls (270 per arm) to detect a difference of 0.5 food groups in the mean dietary diversity score. Along with each AG, we included her parent/primary caregiver (N=540), given that parents and caregivers are usually responsible for purchasing and preparing foods for young adolescent girls.

Additionally, we interviewed school principals (1 per school), main science teacher (1 per school), and HEWs (1 per health post nearest to school). School checklists (1 per school) were conducted to assess any changes in school infrastructure and facilities, materials and supplies, operations, and staffing.

Table 1. Sample sizes

Survey respondent type	Baseline 2019		Endline 2021	
	Intervention	Control	Intervention	Control
Household survey:				
1 Adolescent girl	81	81	270	270
2 Parent/caregiver of adolescent girl	81	81	270	270
School principal/teacher survey or checklist:				
3 Principal (1 per school)	27	27	27	27
4 Science teacher (1 per school)	27	27	27	27
5 School checklist	27	27	27	27
Health worker survey:				
6 HEW (1 per school)	27	27	27	27
Total:	270	270	648	648

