## II. Outcome Measures and Indicators

Outcome measures corresponding to the three research questions are presented below. Outcome measures under RQ 1 includes the primary outcome of the evaluation (i.e., used to test study hypotheses and arrive at a decision on overall study impact and to serve as basis to calculate the sample size); RQs 2 and 3 focus on secondary outcomes.

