### 2.1 Research question 1 (impact on diets of adolescent girls)

For impact estimates, outcome measures related to adolescent diet will be used from the AG dataset only.

Table 2. Outcome measures for RQ1

Outcome	Indicator	Data source
Dietary diversity, consumption of unhealthy foods, and meal frequency	
Primary outcome:
 
 
- Dietary diversity score (# of food groups, out of 10 groups)
 
 
Secondary outcomes:
 
 
- % AG consumed unhealthy foods in past 24h (i.e., sweet foods and sweets, fried and salty foods, and sugar-sweetened beverages)
 
- Mean meal frequency score (# meals or snacks, out of 6 times)
 
	AG survey

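### The SAP drops, without explanation, the second of the two indicators under the protocol's primary outcome: the proportion of girls reaching at least 5 food groups

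*Protocol*

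**What the plan says.** Protocol 2.4 opens its outcome list with "The primary outcome of the study focuses on diet quality measures". Item 1 is dietary diversity among adolescent girls, with two sub-items: (i) the mean number of food groups and (ii) "Proportion of adolescent girls who achieve minimum dietary diversity (at least 5 food groups". The sentence that introduces the secondary outcomes comes after both, so (ii) belongs to the primary outcome.

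The protocol's analysis text (4.4) adds only "Key indicators will include dietary diversity". It does not mention the proportion.

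SAP section II describes the primary outcome as the one "used to test study hypotheses and arrive at a decision on overall study impact and to serve as basis to calculate the sample size". Table 2 then names a single primary indicator, "Dietary diversity score (# of food groups, out of 10 groups". Its two secondary outcomes are consumption of unhealthy foods and meal frequency. Section 3.3 and dummy Table 6 carry the same three outcomes. Tables 3 and 4 cover exposure, delivery and behavioural determinants, and do not list the proportion among girls. The SAP mentions 5 food groups once, in section I, as part of a promoted behaviour.

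**The concern.** An indicator declared under the primary outcome disappears between protocol and SAP with no statement that it was dropped or demoted. Two things are at stake.

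- **Reporting.** If the SAP is followed as written, the proportion is either not reported or reported at discretion once results are known. SAP 1.2 describes the endline survey as already done, and the documents do not show whether data by arm had been seen when the indicator was left out. That is no evidence of selective reporting, but a reader cannot rule it out without a dated explanation.
- **Interpretation.** The programme tells girls to eat from at least 5 groups a day. A difference in mean score does not say how many more girls reach that target. The same mean shift can come from girls well below the threshold or from girls just under it.

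**Working it through.** The defect is textual, so the first step is to trace each indicator through both documents.

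| Place | Mean score | Proportion with at least 5 groups |
|---|---|---|
| Protocol 2.4, primary outcome | yes (i) | yes (ii) |
| Protocol 2.6, sample size | yes | no |
| Protocol 4.4, analysis | generic "Key indicators will include dietary diversity" | not mentioned separately |
| SAP 1.3, sample size | yes | no |
| SAP Table 2, primary or secondary | primary | absent |
| SAP Tables 3 and 4 | not applicable | absent |
| SAP 3.3 list and Table 6 | yes | absent |

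**The plan's own sample size concerns the score only.** Protocol 2.6 gives 189 girls per arm for 0.6 groups, SD 1.40, ICC 0.18, 80% power, alpha 0.05. Two-sided, before clustering: n0 = 2 × (1.40 × (1.960 + 0.842) / 0.6)² = 85.5 per arm. With 27 schools per arm fixed: n = 85.5 × 0.82 / (1 − 85.5 × 0.18 / 27) = 162.9, or 6.03 girls per school. Rounded up to 7, this is 7 × 27 = 189, which matches. SAP 1.3 likewise sizes the trial "to detect a difference of 0.5 food groups in the mean dietary diversity score". Nothing in either document sizes the trial for the proportion.

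**What the proportion could show (illustration only).** The documents give no prevalence or ICC for it. Assumptions: a normal score; mean and SD from protocol 2.6 ("we observed a mean of 3.69, SD: 1.56, categorized as 10 food groups"); a shift of 0.5 groups; a cut at 4.5 as continuity correction for 5 or more; 270 girls per arm, 10 per school; two-sided 5% as in SAP 3.1.

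- Control: 1 − Φ((4.50 − 3.69)/1.56) = 1 − Φ(0.519) = 30.2%.
- Intervention: 1 − Φ((4.50 − 4.19)/1.56) = 1 − Φ(0.199) = 42.1%.
- Difference: 11.9 points.

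Standard error = √[(p0q0 + p1q1) × DE / 270], with DE = 1 + 9 × ICC; power = Φ(difference/SE − 1.96). Protocol 2.6 uses two score ICCs, 0.015 and 0.18. Each is taken in two ways: carried over unchanged, or converted to the binary scale with bivariate-normal scores, as [P(both at or above the cut) − p²]/(pq).

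| Score ICC | Treatment | DE (control / intervention) | SE | Power | 95% half-width |
|---|---|---|---|---|---|
| 0.015 | unchanged | 1.135 | 0.0437 | 78.0% | 8.6 points |
| 0.015 | converted (0.0087 / 0.0094) | 1.078 / 1.085 | 0.0427 | 79.9% | 8.4 points |
| 0.18 | unchanged | 2.62 | 0.0664 | 43.6% | 13.0 points |
| 0.18 | converted (0.107 / 0.114) | 1.960 / 2.025 | 0.0580 | 54.0% | 11.4 points |

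For comparison, the score has SE = √(2 × 1.56² × DE / 270) = 0.143 or 0.217, and power for 0.5 groups of 93.8% or 63.3%.

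Sensitivity: with the cut at 5.0 the proportion goes from 20.1% to 30.2%, and power is 72.7–75.1% at ICC 0.015 and 39.3–50.6% at 0.18. A t reference with 52 degrees of freedom lowers the powers for the proportion at cut 4.5 by about 1–2 points.

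On these assumptions the proportion is less well powered than the score. That argues for a supporting role with an interval, not for leaving it out.

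**The case against.** The strongest reply is that the SAP was right to settle on one primary outcome. The protocol speaks of a single primary outcome but lists two indicators, without saying whether both must succeed or how multiplicity is handled. Only the score has a sample-size basis, and SAP section II ties the primary outcome to that basis. The proportion is a cut of the same 10-group score, so no data are lost and it can be derived at any time. The protocol's declaration of it also still stands, since the SAP nowhere says that it replaces protocol 2.4.

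Much of this stands. Choosing the score as the deciding outcome is sound, and the trial's decision is not affected. But the reply justifies demotion, not silence: the SAP neither demotes the indicator nor explains its absence. Protocol 4.4 does not fill the gap, because it names neither the proportion nor a model specific to it.

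A second objection is that the power figures pair ICC 0.18 with SD 1.56, which the protocol never does; it uses 0.18 with SD 1.40 on 9 food groups. That is correct. With SD 1.40 at ICC 0.18 (mean 3.69, cut 4.5), power is about 51–63% for the proportion and 73% for the score. The conclusion does not depend on either set.

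A third is that a dated note justifying removal would also do. It would cure the traceability problem, but readers would still have no planned estimate for the target that the programme promotes.

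**Conclusion.** The concern holds. One of the two indicators under the protocol's primary outcome has no analysis anywhere in the SAP, and no reason is given. This rests on the text of the two documents and on no calculation. It should be fixed, but it does not threaten the main result: the score analysis and its sample size are unchanged. The shift from about 30% to 42% and the powers of about 78–80% (ICC 0.015) and 44–54% (ICC 0.18) rest on an assumed normal score, an assumed cut and ICCs stated for the score. They illustrate scale and carry no weight in the conclusion. Nothing here shows that the omission was driven by results.

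**What to change.** - Keep the food-group score as the single outcome that decides overall impact, as SAP section II implies.
- Add the percentage of girls reaching at least 5 of 10 groups to SAP Table 2, the section 3.3 list and Table 6, as a supporting indicator that cannot by itself establish impact. It then adds no second route to a positive conclusion.
- Analyse it with the endline linear model with school-clustered standard errors in section 3.3, unadjusted and adjusted. The SAP already plans this model for a binary diet outcome ("AG consumed unhealthy foods in past 24h", reported as a percentage), so no new method is needed.
- Report the percentage-point difference with its 95% interval whatever the score shows.
- Add a dated SAP note stating that this role departs from protocol 2.4, why, and whether endline data by arm had been seen when the decision was made.

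The cost is one variable derived from data already collected, two table rows, one list item and a short note. If the change of role counts as a substantive protocol change, protocol 6.2 sends it to IRB review.
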